7. HYPOTHESIS

We hypothesize that stent retriever thrombectomy will be more efficacious than aspiration or mechanical thrombectomy in thrombus burden reduction as assessed by OCT derived pre-stent thrombus volume (mm³).

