11.6. Study timeline

Stage 1 – Screening, Assent & Randomisation

Participant identification and assent will proceed as described in sections 10 and 11.1.1.1-11.1.1.2 respectively.

- Diagnostic angiography will be performed in the standard manner using appropriate catheters. Heparin will be administered as routinely used for PCI. Angiograms will be reviewed to ensure participation eligibility according to angiographic inclusion/exclusion criteria (section 10.3)
- Once eligibility is confirmed patients will be assented and randomised.

Stage 2 – Baseline assessments

- Once the lesion has been crossed with a coronary guidewire, flow will be established with a 1.5mm semicompliant balloon predilation.
- OCT measurements will be performed using a dedicated OCT catheter over the coronary guide wire in the usual manner for clinical OCT assessment. For Arm 1, the OCT measurements in the baseline assessment will be treated as the pre-stent measurements as thrombus modification will not be performed in this group.

Stage 3 – Post-thrombus modification pre-stent assessments

Patients randomised to Arm 2 (thrombus aspiration) or Arm 3 (thrombus retrieval) will undergo the assessments in this stage.

- Thrombus aspiration (Arm 2) will proceed according to standard clinical practice. In brief, a thrombus aspiration device (i.e. Export Catheter) will be advanced over the coronary guidewire. Aspiration will then proceed.

Date and version No:22/04/2024 v4.0

- Retrieval thrombectomy (Arm 3) will proceed according to the manufacturer's manual. In brief, a microcatheter (e.g. Phenom™, Marksman™) is advanced over the guidewire. Once the microcatheter has traversed the thrombotic occlusion the Solitaire™ X revascularisation device is advanced through the microcatheter until the usable length of the stent extends past each side of the thrombus in the vessel. Then the microcatheter is retracted to the proximal radiopaque marker of the stent. As this retraction occurs the stent self-expands and entangles the thrombus. Next, the microcatheter and Solitaire™ X Revascularisation Device are withdrawn as a unit into the guide catheter under continuous aspiration (Appendix C).
- OCT measurements will be performed using a dedicated OCT catheter over the coronary guide wire in the usual manner for clinical OCT assessment.

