14. STATISTICS

14.1. Number of participants

Based on estimates from previously published work^{9,34} and our stipulation for inclusion of patients with high thrombotic burden, we anticipate a mean pre-stent thrombus volume of 9.6mm³ with a standard deviation estimate of 5.1 mm³ in the standard of care arms. Since this is the first pilot of stent retriever in acute coronary syndromes there is no previous published work that can inform on the expected pre-stent thrombus volume reduction with retriever thrombectomy. We have therefore hypothesised a 33% reduction in mean pre-stent thrombus volume. Using a 1-way pairwise ANOVA with a 2-sided equality, accounting for 2 pairwise comparisons with an α of 0.05, a sample size of 72 patients would have 80% power to detect a 33% reduction in pre-stent thrombus volume with retriever thrombectomy.³⁵ The approach that was used accounts for two pairwise comparisons. Indeed, for one such comparison a sample size of n=48 (n=24 for Arm 1 and 24 for Arm 3) would maintain the desired α of 0.05 and β of 0.2. Given that aspiration thrombectomy was not shown to differ from no thrombus modification,⁹ a sample size of n=48 (n=24 for Arm 2 and n=24 for Arm 3) would maintain the desired α of 0.05 and β of 0.2 for this comparison. The overall sample size is therefore increased by a further n=24 patients for the aspiration thrombectomy group. This leads us to n=72 patients required to show a 33% reduction in pre-stent thrombus burden with a power of 80%. Assuming 12.5% of patients will not have analysable OCT imaging, we plan to enrol 81 patients (n=27 in each group) to ensure the study remains adequately powered.

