14.2. Analysis of Endpoints

In keeping with our usual practice, we will obtain expert statistical advice from the Centre for Statistics in Medicine (or equivalent) for each specific task. A flow diagram detailing number of participants screened and randomised will be provided. Analysis of the OCT-derived primary and secondary endpoints (including angiography-derived) will be conducted offline in a blinded fashion. Summary statistics, including means, medians, and variances, will be calculated at each time point and for each type of data and group (e.g. baseline characteristics, parameters derived from OCT, angiography-derived coronary physiology). The distribution of the levels will be described. For each parameter an analysis of variance will be carried out.

An analysis evaluating for a between group difference in pre-stent thrombus volume will first use an 1-way ANOVA with a 2-sided equality test to assess for an overall trend. Post-hoc analyses exploring the following hypotheses i) retriever thrombectomy (Arm 3) is different to no thrombus modification (arm 1) and ii) retriever thrombectomy (Arm 3) is different to aspiration thrombectomy (Arm 2) will be performed using the Dunnett test. Control of the Type I error at 5% two-sided significance level due to multiple testing will be achieved using Dunnett's method.³⁶ Missing data for the primary analysis will be dealt with complete case analysis if data missingness is <10% (<3 cases per group). If missingness is higher, multiple imputation will be performed instead. Major adverse cardiac and cerebrovascular events will be analysed using proportions statistical testing (Fisher's exact or χ^2 tests), yet they represent an exploratory analysis.

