19.6. Possible risks/discomfort to participants

Patients referred for emergency cardiac catheterization and PCI will undergo this procedure as would routinely be performed. Patients will therefore be informed of the standard of care procedure and its associated risks. All local protocols will be adhered to and only fully trained staff will carry out procedure according to departmental SOPs.

From a research perspective, the PCI procedure time may be lengthened by around 10 minutes to complete the selected study procedures (OCT acquisitions, angiography derived physiology & aspiration/stent retriever thrombectomy). In the context of a PCI procedure that typically lasts approximately 60 minutes. The additional time should not result in any clinically significant difference to the participants. Very occasionally this additional time can result in some back discomfort for patients having to lie on the angiography bed for the additional time period.

Stent-retriever thrombectomy with the Solitaire X revascularisation device is clinically tested and licensed for endovascular intervention in acute ischaemic strokes. Device failure was reported in one case (0.8%) in the two trials that examined this endpoint with no significant sequelae. Device related complications such as arterial dissection or perforation was reported in 5/211 (2.3%) of ischaemic stroke patients randomised to stent-retriever thrombectomy with the Solitaire X revascularisation device. Perforations and edge dissections are encountered in routine PCI practice in 0.37% and 7.7% of patients and interventional cardiologists are familiar with their management. Coronary perforations and significant

Clinical Trial Protocol Template version 15.0

CONFIDENTIAL

© Copyright: The University of Oxford and Oxford University Hospitals NHS Foundation Trust 2019

Page 47 of 57

Date and version No:22/04/2024 v4.0

dissections are usually treated with a stent which is the treatment these patients will eventually receive for their heart attack.

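### Only the device arms can lose the primary endpoint scan because of the allocated treatment, and section 14.2 would drop or blindly impute such patients without using their planned Stage 2 volume

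*Combined protocol and SAP*

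**What the plan says.** The primary endpoint is "OCT derived pre-stent thrombus volume (mm³") (section 7). Section 11.6 plans a Stage 2 OCT in every arm, after the wire has crossed and a small balloon has restored flow. The endpoint scan then differs by arm:

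- Arm 1: "For Arm 1, the OCT measurements in the baseline assessment will be treated as the pre-stent measurements".
- Arms 2 and 3: the endpoint is the Stage 3 scan, after aspiration or retrieval. "Patients randomised to Arm 2 (thrombus aspiration) or Arm 3 (thrombus retrieval) will undergo the assessments in this stage".

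Section 14.2 handles missing primary data in two steps. The first is "Missing data for the primary analysis will be dealt with complete case analysis if data missingness is <10% (<3 cases per group"). The second is "If missingness is higher, multiple imputation will be performed instead". It gives no imputation model, names no analysis population, has no rule for a device step that fails or is abandoned, and does not use the Stage 2 volume in the primary analysis. The primary test is a one-way ANOVA followed by Dunnett comparisons of Arm 3 with Arms 1 and 2.

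Section 14.1 allows for lost scans: "Assuming 12.5% of patients will not have analysable OCT imaging, we plan to enrol 81 patients (n=27 in each group").

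**The concern.** The Arm 1 endpoint is fixed before anything specific to an arm can go wrong. In Arms 2 and 3 the device step stands between randomisation and the endpoint scan. Suppose the device cannot be delivered, fails, or causes a complication, and the procedure goes on to stenting with no Stage 3 scan. The endpoint is then missing because the treatment did not work, which is not the same as an unreadable image.

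The protocol foresees such events. Device deficiency and device-related vessel complications are a co-primary safety outcome (sections 4 and 8), and section 19.6 notes that perforations and significant dissections are usually treated with a stent.

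Dropping these patients changes the question from all randomised patients to those in whom the device step was completed. Imputation need not repair this. A model that knows the arm but not whether the device worked would fill failures with values learned from successes. If failures keep more thrombus than successes, the Arm 3 versus Arm 1 contrast then favours the retriever.

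**Working it through.** **Inputs from the plan (sections 14.1 and 14.2).** For the standard-of-care arms, "we anticipate a mean pre-stent thrombus volume of 9.6mm³", with SD 5.1 mm³. The hypothesised reduction is 33%. There are 27 patients per arm, and 12.5% of scans are expected to be non-analysable.

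**Plan figures reproduced.**
- Effect: 0.33 × 9.6 = 3.168 mm³, so the retriever mean is 9.6 − 3.168 = 6.432 mm³.
- Threshold: 2/27 = 7.4% and 3/27 = 11.1%. The 10% limit and the limit of fewer than 3 per group agree, so complete case can drop at most 2 patients per arm.
- Enrolment: 72 × 1.125 = 81.

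**Which branch applies.** At 12.5%, the expected loss is 27 × 0.125 = 3.4 scans per arm.
- P(3 or more of 27 missing) = 1 − [0.875^27 + 27 × 0.125 × 0.875^26 + 351 × 0.125² × 0.875^25] = 1 − (0.027 + 0.105 + 0.195) = 0.67.
- P(at least one arm reaches 3), with independent arms, = 1 − (1 − 0.673)³ = 0.97.

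On the plan's own assumption, imputation is the likelier route, and its model is not specified.

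**Size under complete case.** The documents give no thrombus volume for failed procedures, so two values are assumed: the control mean (9.6) and the mean plus one SD (14.7). Let k Arm 3 patients be lost with volume v left in place, while the remaining patients average 6.432.

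Arm 3 mean in all randomised = [(27 − k) × 6.432 + k × v] / 27

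| k | v (mm³) | Arm 3 mean | Reduction from 9.6 | Overstatement by complete case | Share of 3.168 |
|---|---|---|---|---|---|
| 0 | – | 6.43 | 33.0% | 0 | 0% |
| 1 | 9.6 | 6.55 | 31.8% | 0.117 | 3.7% |
| 1 | 14.7 | 6.74 | 29.8% | 0.306 | 9.7% |
| 2 | 9.6 | (160.8 + 19.2)/27 = 6.67 | 30.6% | 0.235 | 7.4% |
| 2 | 14.7 | (160.8 + 29.4)/27 = 7.04 | 26.6% | 0.612 | 19.3% |

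In every row complete case would still report 33%.

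**False-positive rate.** This was simulated with no device effect: gamma volumes with mean 9.6 and SD 5.1, 27 per arm, an unadjusted two-sided t-test of Arm 3 against Arm 1, and 5,000 runs. Dropping 2 Arm 3 patients at random gave 4.8%. Dropping them with probability proportional to volume gave 4.7%. Always dropping the two largest volumes gave about 12%.

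**The case against.** The strongest reply is that losing the scan is an inference. Section 11.6 schedules Stage 3 OCT by randomised arm and makes no exception for a failed pass. OCT runs over the coronary guidewire, and section 9 keeps a guidewire beside the retriever. A device that catches nothing therefore does not in itself prevent the scan. The co-primary safety outcome includes complications defined by OCT before stenting, so a scan is part of how they are assessed. All of this stands. A reader might infer that every device failure leaves the analysis, but the documents do not support that. Only failures without a readable Stage 3 scan are affected.

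The number of such patients may also be small. Section 12.2 cites stroke-trial rates of 0.8% for device failure and 2.3% for dissection or perforation. If these carried over to coronary arteries, did not overlap, and always cost the scan, the expected number would be 27 × 0.031 = 0.84. The chance of two or more would be 1 − 0.969^27 − 27 × 0.031 × 0.969^26 = 0.20. Coronary rates may differ, but the documents give none for this device.

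Three further readings go too far:
- That complete case could hide three failures. Three of 27 is 11.1% and goes to imputation.
- That about 30% of the effect could come from the exclusion rule. With the permitted two losses, this needs both at about 19.8 mm³, the mean plus two SD: (160.8 + 39.6)/27 = 7.42, an overstatement of 0.99 mm³, or 31%. Nothing in the documents points to such values.
- That the comparison with aspiration is also tilted towards the retriever. Both arms can lose scans this way, and no document shows that the retriever fails more often.

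Arm 1 can still lose OCT data for ordinary imaging reasons. The asymmetry concerns only loss caused by the device step.

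**Conclusion.** The point holds in a limited form. The endpoint scan follows the device step in Arms 2 and 3 but not in Arm 1. The stated missing-data rule treats a scan lost to treatment failure like an unreadable image, although a Stage 2 volume is planned for that patient.

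Under complete case with the maximum of two such losses in Arm 3, 7% to 19% of the planned effect would come from the rule. This rests on assumed failure volumes of 9.6 and 14.7 mm³ and on both scans being lost through device failure. The simulated type I error stays near 5% unless the lost patients are those with the largest clots. If no scan is lost to device failure, the bias is zero.

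The size under imputation cannot be stated, because the model is not given. Since imputation is the likelier route, its content is the more important gap.

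**What to change.** Amend section 14.2 before outcomes are compared by arm:

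1. Analyse the primary endpoint by randomised arm.
2. Where the allocated device was never deployed and no Stage 3 OCT exists, use the Stage 2 volume as the pre-stent volume, as for Arm 1. Apply this equally in Arms 2 and 3.
3. For other missing Stage 3 scans, specify the imputation model and include Stage 2 volume and device-success status in it.
4. Add two sensitivity analyses: one carrying the Stage 2 volume forward for all device failures or complications without a Stage 3 scan, and one using complete cases.
5. Report missing Stage 3 scans by arm and reason.

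The cost is a few sentences in section 14.2 and one CRF item for the reason a Stage 3 scan is missing. Section 13.3 already records device deficiencies, action taken and outcome. No extra scan is needed.

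There are two limits. Carrying Stage 2 forward assumes no device effect, so it is conservative against the device where some thrombus had been removed. In those cases it therefore belongs only in the sensitivity analysis. A device-success term can be estimated only if some failures have a readable Stage 3 scan. If none do, the sensitivity analyses must show how far the result depends on them.

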4. SYNOPSIS

Trial Title	STENT RETRIEVER THROMBECTOMY FOR THROMBUS BURDEN REDUCTION IN PATIENTS WITH ACUTE MYOCARDIAL INFARCTION		
Internal ref. no. (or short title)	RETRIEVE – AMI study		
Trial registration	NCT05307965		
Sponsor	Oxford University Hospitals NHS Foundation Trust		
Funder	Medtronic & Terumo Inc		
Clinical Phase	Device Pilot		
Trial Design	Randomised controlled trial		
Trial Participants	ST elevation Myocardial Infarction Patients		
Sample Size	n=81		
Planned Trial Period	Start Date: 01/03/2022 End Date: 30/09/2025		
Planned Recruitment period	36 months		
	Objectives	Outcome Measures	Timepoint(s)
Primary	Efficacy of thrombus burden reduction	Thrombus volume (mm ³) (OCT assessment)	Pre-stent
Co-primary	Safety of retriever thrombectomy	• Angiography-/OCT-defined device related target vessel complications, device deficiency	Pre-stent
		• Rate of major adverse cardiac and cerebrovascular events (MACCE)	In hospital 30 days 6 months
Secondary	Efficacy of thrombus burden reduction	Thrombus area, flow area (mm ²) (OCT assessment)	Pre-stent
	Efficacy of thromboatheroma reduction	Thromboatheroma area, flow area (mm ²) (OCT assessment)	Post-stent
	Efficacy of stent implantation	Stent expansion & apposition (OCT assessment)	Post-stent
	Angiographic success rate	TIMI flow, Myocardial Blush Grade, Angiography derived coronary physiology indices	Post-stent
Intervention(s) • Other intervention(s)	Percutaneous coronary intervention with adjunctive use of stent retriever thrombectomy		
Comparator	Percutaneous Coronary Intervention alone or Percutaneous coronary intervention with adjunctive aspiration thrombectomy		

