11.7. Trial Assessments

11.7.1. Data Collection, Patient Reported Outcomes and Clinical Outcomes

Data on the clinical procedures and any devices and/or imaging technologies used will be collected. Medical history will be taken from the patient once informed consent has been given and relevant sections of the medical notes and scans may be accessed by the study team. Clinical outcomes and MACCE will be ascertained at the 6-month telephone follow-up, by accessing relevant sections of the medical records or by contacting the GP if appropriate.

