13.7. Safety Monitoring Committee – Trial Safety Group (TSG)

The Oxford University Hospitals Trust Trial Safety Group (TSG) will conduct a review of all SAEs/SADEs for the trial reported during the quarter and cumulatively. The aims of this committee include:

- To pick up any trends, such as increases in un/expected events, and take appropriate action
- To seek additional advice or information from investigators where required

- To evaluate the risk of the trial continuing and take appropriate action where necessary

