14.3. Interim Safety Analysis

Based on the reported coronary perforation (0.37%), coronary dissection (7.7%) and transient ischaemic attack/ischaemic stroke (0.25-0.8%) rates in contemporary STEMI practice, in a 27-patient arm study, 1 coronary perforation, 1 significant coronary dissection and 1 transient ischaemic attack/ischaemic stroke may be expected by chance. If >2 (>10%) coronary perforation-related SADEs or >2 significant coronary dissection-related SADEs or >2 transient ischaemic attack-/ischaemic stroke-related SADEs occur in the investigational device arm this will be considered too high.

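### MACCE is ranked as a primary safety outcome but gets an exploratory, test-only analysis, and device-related safety events have no analysis suited to counts; at 27 per arm, estimation should carry the safety objective.

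*Combined protocol and SAP*

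**What the plan says.** The synopsis (Section 4) labels safety of retriever thrombectomy co-primary, and Section 8 lists it under primary objectives beside thrombus volume. Both give it two components. The first is "Angiography-/OCT-defined device related target vessel complications, device deficiency", assessed pre-stent. The second is the MACCE rate, in hospital, at 30 days and at 6 months.

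Section 14.2 gives MACCE one sentence. These events "will be analysed using proportions statistical testing", with Fisher's exact and chi-square both offered, "yet they represent an exploratory analysis". It does not say which arms are compared or which time point is tested. It does not mention device-related complications or device deficiency. Its general sentences promise means, medians and variances by group and time point, and an ANOVA for every parameter.

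Everything confirmatory concerns efficacy. The hypothesis in Section 7 is about "thrombus burden reduction as assessed by OCT derived pre-stent thrombus volume". In Section 14.1 the basis is that "a sample size of 72 patients would have 80% power to detect a 33% reduction in pre-stent thrombus volume with retriever thrombectomy". The Dunnett control in 14.2 covers the two thrombus-volume contrasts.

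Safety is also monitored. The Trial Safety Group "will conduct a review of all SAEs/SADEs for the trial reported during the quarter and cumulatively" (13.7). Under 14.3, if more than two SADEs of any of three types "occur in the investigational device arm this will be considered too high".

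**The concern.** An objective can be primary and still be descriptive, but the plan does not say that this one is. One part of the document ranks MACCE with the primary outcomes, and another treats it as exploratory.

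The choice of method matters more than the label. This is an off-licence coronary use of a stroke device (12.2), so readers will look closely at the safety result. The only output 14.2 specifies for MACCE is a p-value from a small comparison. A non-significant p-value under a co-primary heading is easily read as reassurance, although the data may be compatible with considerable excess harm. An interval would show how much harm is excluded, and none is planned. For device-related complications and device deficiency, which bear most directly on the device, no method suited to counts is given.

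**Working it through.** **Step 1. Status and method, side by side.**

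| Component | Rank (Sections 4 and 8) | Analysis in 14.2 | Monitoring (13.6, 13.7, 14.3) |
|---|---|---|---|
| Thrombus volume | Primary | ANOVA, then Dunnett for Arm 3 v 1 and Arm 3 v 2 | n/a |
| MACCE | Co-primary / primary | Fisher or chi-square, called exploratory; no interval, contrast or time point | Quarterly SAE/SADE review; TIA/stroke SADE count |
| Device-related complications | Co-primary / primary | Generic summaries and ANOVA only | Perforation and significant-dissection SADE counts |
| Device deficiency | Co-primary / primary | Generic summaries and ANOVA only | No threshold of its own |

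The rank conflict is therefore confined to MACCE. For the device-related component the gap is one of method. The thresholds count three SADE types in Arm 3 and estimate nothing.

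**Step 2. Inputs.** The documents give no expected MACCE rate, safety margin or safety power, so there is no figure of the plan's own to reproduce. The one input is 27 patients per arm (14.1: 81 in three equal groups). The event counts below are illustrations. Two events is the largest count per event type that does not meet the 14.3 rule.

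**Step 3. Precision for one arm (exact, Clopper-Pearson, 95%).**
- 0/27: upper limit = 1 - 0.025^(1/27) = 0.1277, or 12.8%.
- 2/27 = 7.4%: lower limit = 2.5% quantile of Beta(2, 26) = 0.0091; upper limit = 97.5% quantile of Beta(3, 25) = 0.2429. The interval is 0.9% to 24.3%.

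**Step 4. Precision for a difference (Newcombe, 95%), 2/27 minus 1/27.**
- Difference: 0.0741 - 0.0370 = 0.0370.
- Wilson limits: 2/27 gives 0.0206 to 0.2337; 1/27 gives 0.0066 to 0.1828.
- Lower: 0.0370 - sqrt[(0.0741 - 0.0206)² + (0.1828 - 0.0370)²] = 0.0370 - 0.1553 = -0.118.
- Upper: 0.0370 + sqrt[(0.2337 - 0.0741)² + (0.0370 - 0.0066)²] = 0.0370 + 0.1625 = 0.200.
- Result: +3.7 points (-11.8 to +20.0).

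Fisher's test on the same table gives p = 1.00. With three events in all, the splits 2 v 1 and 1 v 2 are the most probable (each 351 × 27 / 24,804 = 0.382), so every table counts towards p. The test reports nothing, while the interval still allows an excess of 20 points.

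**Step 5. The open choices, a secondary matter.**

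| Events, Arm 3 v comparator | Fisher p | Chi-square p, uncorrected | Chi-square p, continuity-corrected |
|---|---|---|---|
| 4 v 0 | 0.111 | 0.038 | 0.119 |
| 9 v 3 | 0.099 | 0.0495 | 0.102 |
| 10 v 3 | 0.054 | 0.026 | 0.056 |

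The two tests fall on opposite sides of 0.05 only when chi-square is uncorrected, and 14.2 does not say which form is meant. The contrast matters too. For 4/0/0 events in Arms 3/1/2, the exact three-arm test gives 3 × C(27,4) / C(81,4) = 52,650 / 1,663,740 = 0.032, against 0.111 for Arm 3 v either comparator by Fisher.

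**The case against.** The sponsor can fairly say that this is a device pilot, that Section 9 calls the whole trial exploratory, and that 14.2 says the same of MACCE. The hypothesis, the power statement and the error control all concern thrombus volume. That stands. A reader might infer from the co-primary label that a confirmatory safety claim is planned; the documents do not support this. Nor is low power for MACCE a defect, since none is claimed.

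A reader might also infer that the whole safety objective has been demoted. It has not: the exploratory remark refers to MACCE alone, and nothing lowers the rank of device-related complications or device deficiency.

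It would also go too far to say that 14.2 provides nothing for those events. It promises summaries for each type of data, group and time point, has OCT and angiographic endpoints analysed blinded, and 13.1 classifies dissections and perforations. This is partial cover. The examples given are baseline, OCT and physiology data, and means, variances and ANOVA do not describe event counts.

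Finally, a reader might take the test-choice discrepancy as general. It disappears with a continuity correction. In 4 v 0 the expected event count is 2 per arm, where convention already favours Fisher. In 9 v 3 and 10 v 3 one arm must have an event rate of 33% to 37% (9/27 and 10/27), and no document gives a MACCE rate. The open test, contrast and time point would on their own be missing detail only.

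**Conclusion.** The point holds in two parts. First, MACCE is co-primary in the synopsis and primary in Section 8 but exploratory in 14.2, and these must be reconciled. Second, the planned safety analysis does not fit the stated objective: MACCE has significance tests only, and device-related complications and device deficiency have no method suited to counts.

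The size is shown by the precision at 27 per arm. No events at all would still leave rates up to 12.8% compatible with the data, and a 2 v 1 split would leave an excess of up to 20.0 points. These figures assume 27 patients analysed in each arm and illustrative counts. The intervals are wider if patients are lost; the 12.5% allowance in 14.1 is for unanalysable OCT and does not address MACCE follow-up.

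The thrombus-volume analysis is unaffected. The change should be made, because it is cheap and the planned test cannot support a statement about safety.

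**What to change.** **Status.** Give MACCE one status in the synopsis, Section 8 and 14.2, for example a safety objective stated to be descriptive with no confirmatory test. Device-related complications and device deficiency can keep their rank.

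**Analysis, in 14.2.** Make estimation the main safety analysis.
- MACCE: counts per arm with exact 95% CIs, and 95% CIs for Arm 3 minus Arm 1 and Arm 3 minus Arm 2 (Newcombe is one suitable method), at each of the three listed time points.
- Device-related complications and device deficiency, pre-stent: counts with exact 95% CIs in the arm or arms where the device is used. State whether the device means the retriever only or also the aspiration catheter.
- If p-values are kept: Fisher's exact test for the two Arm 3 contrasts, labelled exploratory, with a statement that non-significance is not evidence of safety.

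**Cost.** Wording in three places and simple interval estimates. No new data source is needed: "Clinical outcomes and MACCE will be ascertained at the 6-month telephone follow-up", with medical records and the GP as further sources (11.7.1), and 13.3 records onset dates, from which the earlier time points can be derived. The drawback is that the intervals will be wide, which is an accurate account of what 27 patients per arm can show.
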